4.3.3. Administration of intravitreal triamcinolone acetonide (Triesence)

- Standard preparation as described for intravitreal injections in section 4.3.2.
- Saturate a sterile cotton-tipped applicator with 0.5% proparacaine hydrochloride drops and hold the swab against the planned intravitreal injection site for 10 seconds in preparation for the subconjunctival injection of 1% lidocaine hydrochloride ophthalmic solution for injection (without epinephrine). Alternatively, an injection may be given with just topical anesthesia.
- Use a sterile 4×4 pad in a single wipe to absorb excess liquid and to dry the periocular skin.
- Instruct subject to direct gaze away from syringe prior to intravitreal injection.
- An intravitreal injection using a 30-gauge needle is given 4 mm posterior to the limbus after marking that distance on the ocular surface. Inject medication slowly aiming inferiorly to minimize the dispersal of medication in the visual axis that could affect the patient's vision.
- Place a cotton swab on the site as the needle is injected to help prevent extrusion of medication
- Following the intravitreal injection, patients should be monitored for elevation in IOP
 - Monitoring may consist of a gross assessment of visual acuity
 - Check for perfusion of the optic nerve head immediately after the injection and/or tonometry within 30 minutes following the injection

4.3.4. Administration of dexamethasone implant (Ozurdex)

- Standard preparation as described for intravitreal injections in section 4.3.3 above
- Saturate a sterile cotton-tipped applicator with 0.5% proparacaine hydrochloride drops and hold the swab against the planned intravitreal injection site for 10 seconds in preparation for the subconjunctival injection of 1% lidocaine hydrochloride ophthalmic

solution for injection (without epinephrine). Alternatively, an injection may be given with just topical anesthesia.

- Open the foil pouch over a sterile field and gently drop the applicator on a sterile tray
- Carefully remove the cap from the applicator
- Hold the applicator in one hand and pull the safety tab straight off the applicator; do not twist or flex the tab
- Hold long axis of the applicator parallel to the limbus and engage the sclera at an oblique angle with the bevel of the needle up (away from the sclera) to create a shelved scleral path
- Advance tip of the needle within the sclera for about 1 mm (parallel to the limbus), then re-direct toward the center of the eye and advance until penetration of the sclera is completed and the vitreous cavity is entered; do not advance the needle past the point where the sleeve touches the conjunctiva.
- Slowly depress the actuator button until an audible click is noted. Before withdrawing the applicator from the eye, make sure that the actuator button is fully depressed and has locked flush with the applicator surface.
- Remove the needle in the same direction as used to enter the vitreous
- Following the intravitreal injection, patients should be monitored for elevation in IOP
 - Monitoring may consist of a gross assessment of visual acuity
 - Check for perfusion of the optic nerve head immediately after the injection and/or tonometry within 30 minutes following the injection.⁸²

4.4. Possible side effects and complications of treatments

4.4.1. *Periocular triamcinolone acetonide*

Possible side effects and complications associated with periocular triamcinolone acetonide injections are similar to those associated with intravitreal injections of triamcinolone acetonide, but rates are lower because the drug is not injected directly into the eye.

- Commonly reported events
 - Elevated intraocular pressure
 - Cataract development
- Less frequently reported events
 - Ocular discomfort
 - Transient visual blurring
 - Subconjunctival hemorrhage
 - Ptosis with posterior sub-Tenon's injections (risk increases with multiple injections)
- Rare and serious events
 - Glaucoma or severe IOP elevation requiring surgical therapy
 - Breach of sclera
 - Endophthalmitis (occurs with inadvertent breach of sclera and injection of drug into the eye (less than 1 in 1000 cases))
 - Subretinal deposition of drug
 - Retinal tear with or without retinal detachment
 - Vitreous hemorrhage

4.4.2. Intravitreal triamcinolone acetonide

- Commonly reported events ($\geq 20\%$ of patients)
 - Elevated intraocular pressure in up to 40% of cases
 - Cataract development or progression of existing cataract
 - Subconjunctival hemorrhage
- Less frequently reported events
 - Mild short-term ocular discomfort
 - Short-term visual disturbances
 - Severe increase in eye pressure ($\sim 10\%$ of patients), some of whom may require glaucoma surgery⁸³
- Rare and serious events
 - Endophthalmitis (infectious and non-infectious)
 - Perforation of the globe where there is thinning of the outer covering of the eye
 - Vitreous hemorrhage
 - Retinal detachment
 - Retinal tear

4.4.3. Intravitreal dexamethasone

- Commonly reported events ($\geq 20\%$ of patients)
 - Elevated intraocular pressure which may require medication to lower
 - Subconjunctival hemorrhage
- Less frequently reported events
 - Mild short-term ocular discomfort
 - Short-term visual disturbances
 - Vitreous detachment
 - Headache
 - Cataract development
 - Elevated intraocular pressure which may require surgery to control
 - In eyes with non-intact posterior capsule implant migration to anterior chamber
- Rare and serious events
 - Endophthalmitis
 - Perforation of the globe where there is thinning of the outer covering of the eye
 - Vitreous hemorrhage
 - Retinal detachment
 - Retinal tear
 -

4.4.4. Intravitreal injection

Risks of an intravitreal injection that may be associated with the injection procedure itself have been included along with each type of drug injection above.

5. Adverse event reporting

5.1. Adverse events

Adverse events (AEs) and complications of study treatment will be recorded on study data forms and submitted to the CC. The CC Safety Officer and the DSMC Safety Officer will review all adverse events and make recommendations to the DSMC as to any actions that may be needed.

5.2. Serious adverse events

A serious adverse event (SAE) is an adverse event that results in one of the following outcomes: death, a life-threatening adverse drug experience, inpatient hospitalization or prolongation of existing hospitalization, a persistent or significant disability/incapacity, or congenital anomaly/birth defect. Also, important medical events that may not result in death, be life-threatening, or require hospitalization may be considered a serious adverse event when, based upon appropriate medical judgment, they may jeopardize the patient or subject and may require medical or surgical intervention (treatment) to prevent any of the outcomes previously listed in this definition.

Clinical centers will report all SAEs to the Coordinating Center expeditiously regardless of the relationship to study treatment. When an investigator or clinical center staff member becomes aware of an SAE, it will be reported to the Coordinating Center (CC) within 72 hours with follow up reporting until the event is terminated. The SAE report will include an assessment by the clinical investigator at the managing clinical center as to whether the event is related to treatment. Upon receipt at the CC, the SAE report will be sent to the CC Safety Officer for immediate review and determination as to whether the event meets the criteria for a safety report and whether expedited review by the DSMC Safety Officer is warranted.

All serious and unexpected events possibly related to study treatment will be reported as safety reports to the NEI project officer, the FDA, the pharmaceutical supplier (where appropriate), and all clinical centers in accordance with FDA regulations. The CC and clinical centers will submit all safety reports as expedited reports to their IRBs. Reports of SAEs not deemed to be unexpected will be submitted to the CC's IRB, to the IRB of the clinical center in which the event was reported, as well as to any other study center IRBs which require such reports.

6. Sample size and statistical methods

The primary outcome measurement for the POINT Trial is percent change from baseline in retinal thickness at 8 weeks. The primary analysis will be based on the assigned treatment and all randomized individuals will be included in the analysis (intention-to-treat) with additional sensitivity analyses based on treatment received. Individuals will be randomized to treatment groups, i.e., all eligible eyes from an individual will receive the same treatment.

6.1. Sample size, power and detectable differences

The units of analysis for the primary outcome for POINT are eyes as opposed to individuals. Since we expect approximately 25% of individuals to have bilateral disease, our sample size calculations take advantage of the information from both eyes by incorporating the effect of correlated, multiple measurements from the same individual. To arrive at the target sample sizes, we first calculated the number of independent eyes needed to power a specific aim (i.e. act as though each participant had only one study eye) and then used the following adjustment to calculate the required number of individuals:

$$NS = NIE * [(1 + r) / (2*p + (1+r)(1-p))]$$

where NS denotes the required number of individuals, N_{IE} denotes the number of independent eyes, p denotes the percentage of individuals with bilateral disease (and so two study eyes), and r denotes the correlation between eyes⁸⁶. Estimates for the correlation (r) between outcome measurements for an individual are based upon preliminary data from the MUST Trial and FS.

Power calculations for the primary hypotheses are based upon pair-wise comparisons of the three treatment arms: intravitreal injection of triamcinolone, dexamethasone pellet, and periocular injection of triamcinolone. A Bonferroni correction will be used to adjust for multiple comparisons, i.e. a two-sided type I error rate of $0.05/3 = 0.01667$ will be used to determine statistical significance. The sample sizes needed to provide 90% power for the superiority hypotheses (intravitreal injection or dexamethasone pellet versus periocular injection) and 80% power for the non-inferiority hypothesis (intravitreal injection versus dexamethasone pellet) were computed separately for each comparison and then the maximum sample size was selected. The primary outcome is the change in retinal thickness at the central subfield at 8 weeks. Given the skewness in the distribution of retinal thickness, a log-transformation will be used to analyze the primary outcome^{74, 87}; hence, the comparisons will be represented on a relative scale (i.e. percent of baseline) and transformed to obtain the percent change from baseline. A 20% change in retinal thickness is associated with clinically meaningful changes in visual acuity.⁷⁴ In the MUST Trial, approximately 25% of individuals had bilateral macular edema and the correlation between-eyes was 0.40 for log retinal thickness.^{4, 6} The standard deviation for change in log retinal thickness was approximately 0.33 in the MUST Trial; a conservative estimate since the treatment of macular edema was not standardized and the timing of the assessment, at 6 months after randomization, was not linked to the implementation of treatment for macular edema. Based upon the 6-month OCT evaluation in the MUST Trial, we allowed for a 10% loss to follow-up.

For the first two superiority hypotheses, we evaluated the power to show that each of the treatment methods for intravitreal corticosteroids (triamcinolone injections and dexamethasone pellets) is superior to periocular triamcinolone injections at 8 weeks. In previous studies, treatment with the dexamethasone pellet has resulted in a decrease in retinal thickness of 30%-

50%, so a 40% decrease or log change in retinal thickness of $\log(0.60) = -0.5108$ was selected. Intravitreal triamcinolone is expected to have a similar level of improvement; whereas periocular triamcinolone is expected to have a smaller but clinically meaningful change, i.e. a 25% reduction or log change of $\log(0.75) = -0.2877$. Based upon a standard deviation of log-retinal thickness of 0.33, a sample size of 89 independent eyes per treatment group, i.e. 89 individuals with one eye for each individual, provides 98% power to detect a 40% reduction in retinal thickness for an intravitreal corticosteroid treatment as compared to a 25% reduction for periocular triamcinolone at 8 weeks with a two-sided type I error rate of 0.01667 (i.e. 0.05/3). This number increases to 99 individuals after inflating it for a 10% loss to follow-up. By including outcomes from both eyes for participants with bilateral macular edema (assuming a between eye correlation of 0.4 and 25% bilateral disease), we can reduce our sample size to 89 individuals enrolled in each arm (267 total). That is, 10 fewer participants per arm after accounting for losses to follow-up than are required if we only include a single eye per participant.

For the third hypothesis, we evaluated the power to show that the dexamethasone pellet is non-inferior to injected triamcinolone. Previous research has indicated that the threshold for reproducibility is 10% and that a 20% change is associated with changes in visual acuity.^{74, 88} Therefore, we chose a non-inferiority margin of 10%, i.e. we would consider the dexamethasone pellet to be non-inferior if the percent reduction in retinal thickness was 30% or more ($\log[0.7]$) as opposed to a 40% ($\log[0.60]$) in the intravitreal injection group, i.e. the difference in the log retinal change was at most 0.15 ($\log[0.7] - \log[0.6]$). A sample size of 89 independent eyes per treatment group will provide 80% power to demonstrate non-inferiority with a one-sided type I error rate of 0.01667. We would reject the null hypothesis of inferiority if the upper bound of the 96.7% confidence interval of the difference in log retinal change from baseline at 8 weeks was less than 0.15 ($\log[0.7] - \log[0.6]$) or equivalently if the ratio of the percent of baseline for the two groups was less than 1.16 (0.7/0.6). Assuming a between-eye correlation of 0.4, 25% bilateral disease, and a 10% loss to follow-up, we will need to enroll 89 individuals in each treatment arm to attain 80% power, i.e. the inclusion of both eyes for bilateral disease off-sets the sample size inflation necessary to account for losses to follow-up.

An important secondary outcome for the comparison of intravitreal triamcinolone injection versus the dexamethasone pellet will be change in IOP. In prior studies, treatment with intravitreal triamcinolone resulted in IOP elevation for 40% of study eyes.^{33, 51} In contrast, reports of IOP elevation with dexamethasone pellet have been more variable but consistently lower, ranging from 5% to 17%.^{62, 68} A sample size of 89 independent eyes per treatment group, which is equivalent to 89 individuals per arm allowing for bilateral disease and losses to follow-up, will provide 99% power to detect an increase in the percent of eyes with an IOP elevation from 12% in the dexamethasone pellet arm to 40% in the intravitreal triamcinolone injection arm with a 2-sided, type I error rate of 0.05.

Clinical resolution is one of the standard outcomes in macular edema trials. Based upon the MUST Trial and other research, this improvement likely represents a measureable reduction in OCT measurement rather than complete resolution.^{4, 6, 74, 89} A single PST triamcinolone injection resulted in clinical improvement for 50-55% of eyes between one and three months.^{30, 46} Intravitreal triamcinolone and the dexamethasone pellet are expected to result in improvements of 35% and 25%, respectively. Based upon the assumptions outlined above, the sample size of 89 independent eyes per treatment group, which is equivalent to 89 individuals per arm allowing for bilateral disease and losses to follow-up, would allow us to detect an increase from 50% to 85% or 75% with 99.9% or 93% power, respectively, assuming a 2-sided type I error rate of 0.05 for this important secondary outcome.

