6.2. Statistical methods

The primary analysis will adhere to the intention to treat principle regardless of treatment deviations made either in error or per the best medical judgment of the treating ophthalmologist. Evaluation of continuous outcomes over time (such as log change in retinal thickness or best corrected visual acuity) and binary outcomes over time (such as normal/abnormal IOP) will use a repeated measures analysis with Gaussian or logit links that account for the nested correlations between observations over time and between eyes of the same patient.⁹⁰ A saturated mean model, including visit and visit by treatment interaction terms, will be used. An unstructured covariance matrix will be used to model the within-eye repeated measurements augmented by random effects to induce cross-sectional between-eye associations. Alternatives, including a first-order, auto-regressive process (an AR(1) model) along with a random intercept, will be considered if the unstructured covariance model is unstable. This structure allows for correlation to decrease with increasing time-separation down to a level set by the random intercept.

Significance for superiority hypotheses in POINT will be determined by comparing the p-value of the interaction term for the week 8 visit with 0.01667 (i.e. 0.05/3). Significance for the non-inferiority hypothesis in POINT will be assessed by comparing the upper bound of the 96.7% confidence intervals for estimate of the difference in change in log retinal thickness at 8 weeks, which is estimated by the 8-week interaction term, with the defined non-inferiority boundary of 0.15 on the log scale, which is equivalent to a 10% difference in percent reduction (40% vs 30% reduction) for the two groups.

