POINT has a focused set of primary research questions and related analyses. Bonferonni corrections will be applied to control the type I error rates for the primary hypotheses within each study. However, a large number of comparisons are planned for secondary outcomes and caution is needed in the reporting of interpretation of the results. Our primary focus for analyses of these outcomes will be on the parameter estimates and confidence intervals as opposed to p-values as recommended by Wang et al⁹⁴. Several methods of adjusting P-values for multiple comparisons exist, however no clear consensus as to the most appropriate method is available and it is difficult if not impossible to quantify ahead of time the number of comparisons that will be performed. In general, issuing cautions is sufficient, but for identifiable and related sets of

estimates we will do adjustments. We expect that related sets of estimates will have a high positive correlation, making a Bonferroni correction extremely conservative. Therefore, we will estimate the covariance matrix for these related sets using a bootstrap approach and also estimate the null distribution of the minimum P-values for the multivariate distribution of Z-scores using a global null hypothesis permutation distribution.

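### Single-step Bonferroni for the three primary hypotheses is valid, but a capped Holm step-down would raise non-inferiority power from about 82% to 86% under the same 0.05 familywise limit

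*Combined protocol and SAP*

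**What the plan says.** Section 2.2 lists three primary hypotheses: intravitreal triamcinolone superior to periocular, dexamethasone superior to periocular, and dexamethasone non-inferior to intravitreal triamcinolone.

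- **Multiplicity (6.1):** "A Bonferroni correction will be used to adjust for multiple comparisons, i.e. a two-sided type I error rate of" 0.05/3 = 0.01667. Section 6.2 adds that Bonferroni "corrections will be applied to control the type I error rates for the primary hypotheses within each study". No step-down or gatekeeping procedure is named for the primary hypotheses.
- **Superiority (6.2):** "Significance for superiority hypotheses in POINT will be determined by comparing the p-value of the interaction term" at week 8 with 0.01667.
- **Non-inferiority (6.1):** 89 independent eyes per arm are said to give "80% power to demonstrate non-inferiority with a one-sided type I error rate of 0.01667". Inferiority is rejected if the "upper bound of the 96.7% confidence interval of the difference in log retinal change from baseline at 8 weeks was less than 0.15". Section 6.2 repeats the rule: "comparing the upper bound of the 96.7% confidence intervals" with 0.15 on the log scale.
- **Power targets (6.1):** 90% for the superiority comparisons but "80% power for the non-inferiority hypothesis (intravitreal injection versus dexamethasone pellet) were computed separately for each comparison".

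**The concern.** Non-inferiority has the lowest power target of the three primary hypotheses. Under the design assumptions it is the one most likely to fail by chance, in about 18% of trials. Single-step Bonferroni never passes on level from hypotheses already rejected, so non-inferiority is held at one-sided 0.01667 even when both superiority tests have succeeded. A step-down on the same p-values has the same familywise guarantee and can only add rejections.

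The plan contains no error in its error control here. What is at stake is avoidable loss of power and thin protection of the 80% target if variability or dropout is somewhat worse than assumed.

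There is also a wording point. Section 6.1 attaches the two-sided label to 0.01667 for all comparisons, whereas its non-inferiority paragraph uses that level one-sided, and the 96.7% interval in 6.1 and 6.2 agrees with one-sided use.

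**Working it through.** **Inputs (all section 6.1 unless noted).** SD of change in log thickness 0.33; margin 0.15 (also 6.2); both intravitreal arms at a 40% reduction, log 0.60; periocular 25%, log 0.75; 89 individuals per arm; 10% loss; 25% bilateral; between-eye correlation 0.40; allocation 1:1:1 (3.1).

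**Reproducing the plan.** With 89 independent eyes, power = Φ(0.15 / (0.33 × √(2/89)) − 2.128) = 81.7%, against the stated 80%. The 40% vs 25% superiority comparison at two-sided 0.01667 gives 98.3%, against the stated 98%. Reading non-inferiority as two-sided 0.01667 (one-sided 0.00833) gives 73.8%, so the 80% holds only with the one-sided reading.

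**Effective sample size.** 89 × 0.9 × (2 × 0.25 + 1.4 × 0.75) / 1.4 = 88.68 eyes per arm. SE = 0.33 × √(2/88.68) = 0.0496.

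**Closed-form non-inferiority power at 88.68 eyes.**

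| One-sided level | Power | Largest observed log difference that passes |
|---|---|---|
| 0.01667 (plan) | 81.6% | 0.0445 |
| 0.025 (cap) | 85.7% | 0.0529 |
| 0.05 (uncapped Holm, last step; not proposed) | 91.7% | 0.0685 |

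**Why no plan rejection is lost.** Holm compares the ordered p-values with 0.01667, 0.025 and 0.05. Its first threshold equals the plan's, later ones are larger, and the cap of 0.025 exceeds 0.01667. Holm controls familywise error at 0.05 under any dependence, and the cap only removes rejections, so the limit holds.

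**Joint simulation.** The three contrasts share arms; normal tests, 2,000,000 trials per scenario.

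| Scenario | Non-inferiority: plan → capped Holm | All three: plan → capped Holm |
|---|---|---|
| Periocular 25% (design) | 81.6% → 85.7% | 79.5% → 85.0% |
| Periocular 30% | 81.6% → 85.4% | 54.6% → 69.4% |
| Periocular 32% | 81.5% → 84.7% | |
| Periocular 35% | 81.6% → 83.1% | |
| Periocular 40% | 81.6% → 81.7% | |
| SD 0.30 (assumed) | 88.5% → 91.5% | |
| SD 0.36 (assumed) | 74.1% → 79.2% | 69.6% → 77.4% |

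In the design scenario both superiority tests succeed under the plan in 96.8% of trials, so the larger level is nearly always available. Rejections under the plan lost by capped Holm: none in any scenario.

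**Equivalent sample size.** Bonferroni non-inferiority power is 81.6% with 89 individuals per arm, 85.6% with 99 and 86.0% with 100. Matching 85.7% takes about 100 per arm, or 3 × (100 − 89) = 33 more participants.

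**Protection of the 80% target.** The largest SD that keeps 80% power is 0.336 under the plan and 0.356 at one-sided 0.025. With 15% loss (assumed), power is 79.2% against 83.7%; with 20% loss (assumed), 76.6% against 81.4%.

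**Actual error, plan → capped Holm.**

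- False non-inferiority, dexamethasone at the margin, periocular 25%: 1.7% → 2.4%.
- Familywise, all arms equal: 3.1% → 4.1%.
- Familywise, dexamethasone at the margin and equal to periocular: 3.2% → 3.9%.
- Familywise, one superiority null true and the other two hypotheses certain wins (worst case found): 1.7% → 5.0%.

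**Interval form.** Using the 96.7% interval when no superiority test is rejected at 0.01667, and the 95% interval once at least one is, agreed with capped Holm on non-inferiority in every simulated trial. In the design scenario, non-inferiority is declared while the 96.7% upper bound is at or above 0.15 in 4.12% of trials, which is 0.0412 / 0.8571 = 4.8% of declarations.

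**The case against.** The strongest reply is that nothing is broken. The plan asks for 80% and delivers about 82%, with one fixed interval that decides non-inferiority. Choosing another valid scheme is partly preference. That stands, and it is why this is an improvement to consider and not a correction.

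**Timing and credibility.** The trial is open-label to physicians and patients (3.1). The Coordinating Center draws up the randomization schedules (3.7) and prepares monitoring reports with outcome data by treatment assignment (7.2.4). The documents do not say who would write such a change, or whether those people are kept from by-arm data. Loosening a primary criterion mid-trial would be challenged if they are not. This stands as a condition on adopting the change; it does not defeat the proposal.

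**A looser standard on the same data.** This is true. After a superiority win, the largest passing difference moves from 0.045 to 0.053. False non-inferiority at the margin rises by about 44% in relative terms (0.0242 / 0.0168), and roughly 1 declaration in 20 would sit beside a 96.7% interval that reaches 0.15. The test is never looser than one-sided 0.025.

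**Choice of scenarios.** Section 6.1 calls the SD of 0.33 conservative. A smaller SD shrinks the gain to 3 points at 0.30, but it stays positive. Using the unrounded margin log(0.7/0.6) = 0.154, power with 89 eyes is 83.8% against 87.6%, and at 15% loss Bonferroni gives 81.5%, so the shortfall there depends on the rounded 0.15. Section 6.2 does use 0.15.

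**Conditional gain.** The non-inferiority gain needs a superiority win. It is 1.5 points at a 35% periocular reduction and about 0.1 at 40%. At 30%, each superiority test has about 76% power under the plan, so non-inferiority is then no longer the weakest hypothesis; the step-down lifts those tests too, to about 84–85%.

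**Conclusion.** The point holds as a low-cost improvement to a valid plan. Under the design assumptions, capped Holm cuts the chance of missing non-inferiority from about 18% to about 14%. It raises the chance of winning all three primary hypotheses by 5.5 points, loses no rejection the plan would make, and stays within the 0.05 familywise limit.

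The figures rest on SD 0.33, margin 0.15, equal intravitreal arms at a 40% reduction, 88.7 effective eyes per arm and normal tests. The size of the non-inferiority gain depends on how far periocular treatment falls short. The stated 80% and 98% power figures remain correct as lower bounds. The sidedness wording changes no result.

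**What to change.** In sections 6.1 and 6.2, replace the single-step rule with:

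> The three primary hypotheses are tested by Holm's procedure at familywise 0.05, with two-sided p-values for superiority and the one-sided p-value for non-inferiority. Ordered p-values are compared with 0.01667, 0.025 and 0.05, stopping at the first failure. Non-inferiority is not declared if its one-sided p-value is 0.025 or more.

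State the interval form for non-inferiority as well: the upper bound of the 96.7% interval must lie below 0.15 if neither superiority test is rejected at 0.01667, and that of the 95% interval once at least one is. Report the 96.7% interval alongside in every case.

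Adopt this only if those making the change have not seen results by treatment arm, and record that fact. If that cannot be shown, keep Bonferroni; the 80% power statement stands.

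Either way, limit the two-sided label in the multiplicity paragraph of 6.1 to the superiority tests.

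**Cost.** SAP wording only: sample size, visits and data collection do not change. The statistical price is the higher actual error shown above, a deciding interval whose level depends on the superiority results, and no simple simultaneous intervals.

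### Does describing the 0.15 log margin both as a ratio of 1.16 (0.7/0.6) and as a 10% difference make the non-inferiority rule wrong or ambiguous?

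*Combined protocol and SAP*

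**What the plan says.** Section 6.1 introduces the margin in percentage terms: "Therefore, we chose a non-inferiority margin of 10"%, explained as a reduction of at least 30% with the implant against 40% with intravitreal triamcinolone. It then moves to the log scale, where "the difference in the log retinal change was at most 0.15", with log(0.7) minus log(0.6) printed as the source. It restates the rule as a ratio: "or equivalently if the ratio of the percent of baseline for the two groups was less than 1.16 (0.7/0.6").

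Section 6.2 gives the analysis rule. The upper bound of the 96.7% confidence interval for the week-8 difference in log change is compared "with the defined non-inferiority boundary of 0.15 on the log scale". It adds the gloss "non-inferiority boundary of 0.15 on the log scale, which is equivalent to a 10% difference in percent reduction (40% vs 30% reduction").

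The planning values are in section 6.1. Earlier work reported that "treatment with the dexamethasone pellet has resulted in a decrease in retinal thickness of 30"% to 50%; a 40% decrease was selected, and "Intravitreal triamcinolone is expected to have a similar level of improvement".

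**The concern.** The margin is the decision threshold for a primary hypothesis, so it should have one value and one meaning. Two features suggest that it does not.

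First, one sentence in 6.1 carries three numbers that are not identical: 0.15, 1.16 and 0.7/0.6. A confidence limit falling between the smallest and the largest would pass under one expression and fail under another.

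Second, the margin is argued for in percentage points but applied as a ratio. If triamcinolone does not reduce thickness by about 40%, the test does not apply a 10-point margin. If triamcinolone does worse than planned, the test tolerates more than 10 points, and a reader could take a successful result as a stronger claim than was tested. At a 30% triamcinolone reduction the boundary corresponds to an 18.7% implant reduction. That is just under the 20% change for which section 6.1 states: "A 20% change in retinal thickness is associated with clinically meaningful changes in visual acuity".

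**Working it through.** **Inputs (section 6.1):** SD of log change 0.33; 89 independent eyes per arm; one-sided alpha 0.01667 (z = 2.128); true difference zero, since both intravitreal arms are expected to behave alike; 96.7% interval.

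**The plan's power.** SE = 0.33 × √(2/89) = 0.0495. Power = Φ(margin/SE − 2.128). For a margin of 0.15 this is 0.8171, or 0.8118 with the noncentral t. The stated 80% is reproduced.

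**The three expressions of the boundary.** Eyes per arm for 80% power are from the normal approximation, then the t calculation.

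| Expression | Ratio | Log | Power, 89 eyes | Eyes for 80% |
|---|---|---|---|---|
| 1.16 | 1.1600 | 0.1484 | 0.8085 | 88 / 89 |
| 0.15 | 1.1618 | 0.1500 | 0.8171 | 86 / 87 |
| 0.7/0.6 | 1.1667 | 0.1542 | 0.8385 | 81 / 82 |

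To two decimals, 0.15 and 1.16 agree, because exp(0.15) = 1.162. Only the bracketed 0.7/0.6 does not: it rounds to 1.17. The likely sequence is that 0.1542 was rounded to 0.15 and the rounded value was then exponentiated. The whole spread is 0.1542 − 0.1484 = 0.0058 log units, about 12% of one standard error. With no true difference, the upper limit would fall in that window in about 3% of trials (0.8385 − 0.8085).

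**Percentage points allowed by 0.15.** With triamcinolone reduction R, the allowance is 100 × (1 − R) × (exp(0.15) − 1).

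| R | Points allowed | Implant reduction at the boundary |
|---|---|---|
| 50% | 8.1 | 41.9% |
| 45% | 8.9 | 36.1% |
| 40% | 9.7 | 30.3% |
| 35% | 10.5 | 24.5% |
| 30% | 11.3 | 18.7% |

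The allowance is exactly 10 points at R = 1 − 0.10/0.16183 = 38.2%. At the planned 40%, 0.15 is slightly stricter than 10 points.

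**What the implant would have to show.** The last column is where the upper confidence limit may reach; it is not a result that would pass. The half-width is about 2.128 × 0.0495 = 0.105, so the observed log difference must be below about 0.15 − 0.105 = 0.045.

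- At an observed triamcinolone reduction of 30%, the implant must show at least 1 − 0.70 × exp(0.0447) = 26.8%.
- At 40%, it must show at least 1 − 0.60 × exp(0.0447) = 37.3%.

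The observed shortfall that still passes is therefore about 3 points, not 11.

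**The case for a change.** The best case for a change is that the margin is justified on the percentage scale, by reproducibility at 10% and an acuity link at 20%, and that results will be transformed to percent change. Readers will therefore see percentages beside a 10% margin that the test does not apply uniformly. The 40% versus 30% example is a planning value, whereas the test runs at whatever reduction is observed, and neither section says that the equivalence depends on it. A rewording would cost almost nothing.

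The arithmetic behind this stands, and the text could have been more explicit. Three things limit its force.

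- The example is printed with the 10% reading in both sections, and 6.1 says that comparisons are on a relative scale. Anchoring a relative margin at an expected value is ordinary practice, and the plan nowhere claims that 10 points holds at every triamcinolone result.
- The 30% to 50% range comes from earlier implant studies. Triamcinolone at 30% is a stress case, and there the excess over 10 points is 1.3. From 40% to 50% the boundary is stricter than 10 points.
- The comparison with the 20% threshold does not carry over. Sections 3.3, 3.5 and 4.2.3 apply that figure to individual eyes, while the boundary concerns a difference between group means. An implant result near 18.7% would also fail the test on the planned precision.

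**Conclusion.** No change is needed. The bracketed 0.7/0.6 is a clerical rounding slip of about 0.4% on the ratio scale. The 10% is an approximate reading at a stated planning value. The operative rule is unambiguous: the upper 96.7% limit for the log difference must be below 0.15, as both 6.1 and 6.2 state. That limit is a little stricter than the exact log(0.7/0.6). An analyst following the plan would use 0.15 and reach the same conclusion with or without new wording.

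Over triamcinolone reductions of 30% to 50%, the allowance runs from 11.3 to 8.1 points, against a nominal 10. Power is at least 80% under every expression, so 89 eyes per arm is adequate whichever is taken.

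The power and observed-difference figures assume the plan's SD of 0.33 and 89 independent eyes per arm; the power figures also assume no true difference between the intravitreal arms. A different SD would move those figures, but not the finding that the three expressions nearly coincide.
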